## 21. Who will have access to your study data / biospecimens?

- ☒ Brown PI and other Brown research team members (including advisor).

### **Describe how unauthorized access by others will be prevented.**

Stronghold is a secure virtual compute environment designed for remotely analyzing sensitive data. It uses encrypted SSH (Secure Shell) with two-factor authentication for remote access. Access to each virtual network is limited to a single PI and any additional students or staff who the PI authorizes in writing to CIS. The PI enters into a written agreement with CIS that authorized users must comply with all necessary training requirements. CIS staff who have access to Stronghold have completed CITI course modules for working with human subject data as required by Brown's Office of Research Protection.

Stronghold is accessible only from within the Brown campus network and by Virtual Private Network connections (using two-factor authentication) from outside the campus network. All network connections to Stronghold pass through at least two firewalls: a dedicated firewall on the Brown campus network and a host-based firewall in the Stronghold environment. The Stronghold system is physically located in a locked rack in a CCTV monitored data center on the Brown campus. Only certain authorized CIS staff have access to this locked rack. Entry to the data center is limited to authorized Brown IT personnel and their guests, and all entries are logged.

The Stronghold system is physically located in a locked rack in a CCTV monitored data center on the Brown campus. Only certain authorized CIS staff have access to this locked rack. Entry to the data center is limited to authorized Brown IT personnel and their guests, and all entries are logged.

All data transfers to and from Stronghold take place through a staging area accessed with the SCP (Secure Copy) protocol using two-factor authentication. Once uploaded, data is only accessible from virtual machines within the Stronghold system. Data must be explicitly moved into the staging area by the PI (or anyone the PI authorizes in writing) before it can be downloaded. All transfers are logged and audited, and real-time alerting can be enabled at the PI's request. All analyses and data will take place and remain on Stronghold. Research collaborators external to Brown must be credentialed through Brown University with explicit written authorization from the PI.

Only authorized research team members will have access to the Google Firestore, Qualtrics,

Zoom, Daily Transcription, and Dedoose accounts. In addition to the AES 256 bit encryption of data within Google Firestore, only designated research staff and CIS staff will have access to the account. The focus group and key informant interview audio files will be uploaded by Brown staff to a password-protected folder on Brown School of Public Health departmental servers, only accessible to designated study staff, before uploading the files to Daily Transcription. All original transcripts will be stored on the Departmental Server, and de-identified transcripts from Daily Transcription will be managed/analyzed in Dedoose.

- ☐ Data will be shared with research collaborators external to Brown.

**Describe how you will securely share / transfer the data outside of Brown.**

Click or tap here to enter text.

- ☐ Data will be shared with a data repository.

**Describe how you will securely share / transfer the data outside of Brown.**

Click or tap here to enter text.

## PROVIDENT Data and Safety Monitoring Plan

### Study Title: Reducing Overdose Mortality Using Predictive Analytics: A Randomized, Statewide, Community Intervention Trial

#### A. Summary of the Protocol

##### Study Design

This randomized, community-level intervention trial aims to develop a predictive analytics model that forecasts future overdose mortality. This tool, called **PROVIDENT (Preventing Overdose using Information and Data from the Environment)**, will be used to identify neighborhoods at high risk of future overdose outbreaks. The study will use a randomized design to inform a community-level overdose prevention approach in neighborhoods at high risk of overdose outbreaks.

This study will be conducted in two phases. In phase I (Specific Aim 1), we will develop a predictive analytics model to forecast future overdose mortality at the neighborhood level, defined as census block groups. There are 809 populated census block groups in Rhode Island, grouped in 39 cities/towns. We will use a spatiotemporal machine learning approach, in which the outputs of multiple classification and spatial-temporal machine learning prediction models are combined based on minimizing cross-validated risk.

In phase II (Specific Aim 2), we will conduct a randomized, statewide, policy intervention trial to evaluate whether prioritizing interventions to neighborhoods identified by the PROVIDENT model as being at highest risk of overdoses is more effective at reducing city-level overdose burden than a non-prioritized intervention approach. The primary outcome of the PROVIDENT trial will be city/town-level fatal and non-fatal overdose rates, measured from six months after the interventions have been implemented. Therefore, the trial will be randomized at the level of the city/town, rather than at the level of the individual.

##### Primary and Secondary Outcome Measures

We will evaluate, at the city/town level, whether prioritized intervention deployment to neighborhoods at high risk of future overdose reduces population-level overdose morbidity and mortality. The primary outcome of the trial will be the cumulative incidence of fatal and non-fatal overdose at the city/town level during the study period. While the PROVIDENT model only forecasts future overdose deaths, we will include a composite measure of municipal-level fatal and non-fatal overdose events as the primary end-point in the trial to ensure adequate power. We will compare fatal and non-fatal overdose rates in the treatment and control municipalities, allowing for a 6-month ramp-up period to allow time for the targeted interventions to be implemented.

Fatal overdoses will be defined as drug-related deaths deemed unintentional by the state medical examiner. Specifically, we will include all deaths that: (1) occur in a Rhode Island municipality; (2) the final manner of death was deemed an accident; and (3) a drug is listed on the death certificate as the primary cause of death or a significant contributing factor. The state-wide nature of Rhode Island's centralized medical examiner system means that all accidental deaths are investigated in a similar and consistent manner (including robust toxicological analyses, death scene investigation, and autopsy by a medical professional); all deaths are certified by the chief medical examiner, resulting in a highly reliable reporting system.

Non-fatal overdoses will be defined as emergency medical services (EMS) runs for suspected non-fatal opioid overdoses identified and classified using the Rhode Island Department of Health-modified Council of State and Territorial Epidemiologists (CSTE) case definition. These data are captured in the Rhode Island Emergency Medical Services Information System (RI-EMSIS) and validated by the Rhode Island Department of Health (RIDOH). The 2022 CSTE guidance identifies suspected nonfatal opioid overdoses when an EMS run meets any of 4 criteria: (1) the provider's primary impression or provider's secondary impression is opioid overdose-related, OR (2) the primary symptom or other associated symptoms is opioid overdose-related, OR (3) medication administered is naloxone and response to medication administered is improved, OR (4) the

patient care report narrative contains (a) at least 1 opioid-related keyword and (b) at least 2 overdose-related keywords. Based on this new standard guidance, in 2023, RIDOH updated its existing criteria for suspected nonfatal opioid overdose-related EMS case definition to align with CSTE guidance. The RIDOH-modified CSTE case definition uses five criteria to classify a nonfatal opioid overdose-related EMS run, where EMS records are flagged if any of the following criteria were met: (1) Primary/secondary impressions of the patient are opioid-related, and Narcan was given, OR (2) Primary/secondary impressions of the patient are opioid-related and mention Narcan or unresponsive term in the narrative report, OR (3) Narcan was given, and patient condition improved, OR (4) Mention of Narcan and at least two overdose-related keywords in the narrative report, OR (5) Narcan was given to the patient prior to EMS arrival. This RIDOH-modified CSTE case definition has been validated against the RIDOH original definition and CSTE-guided definition, and the modified case definition had a positive predictive value of 91.5% in identifying nonfatal opioid overdose-related EMS incidents ([Enhanced Emergency Medical Services Case Definition to Identify Suspected Nonfatal Opioid Overdose-Related Incidents in Rhode Island](#)). *Data from 2016 to the present have been updated by RIDOH with the new case definition, ensuring consistency, fidelity, and reliability of this case definition for the primary outcome measure.*

In exploratory analyses, we will examine the effect of the intervention on overdose fatalities and non-fatal overdoses separately to determine whether the intervention produced similar changes in rates of each outcome, and/or produced shifts in the distribution of fatal and non-fatal events without affecting the overall incidence rate. We will also examine the effect of the intervention on overdose fatalities and non-fatal overdoses separately and as a composite using the location of residence of the individual who overdosed rather than the incident location.

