trial will be annual city/town-level overdose rates, measured from six months after the interventions have been implemented. Data collection methods will include a continuation of secondary data transfers with RIDOH and analyses established in Phase 1. We will evaluate, at the city/town level, whether targeted intervention deployment to neighborhoods at high risk of future overdose reduces population-level overdose morbidity and mortality. Fatal overdoses will be defined as accidental drug-related deaths deemed by a medical examiner to be attributed to a prescription or illicit drug. Non-fatal overdoses will be defined as ED visit for a suspected overdose reported through the state's 48-Hour Overdose Reporting System.

[figure not shown]

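### The SAP counts deaths from any drug but non-fatal events for suspected opioid overdose only, so the exploratory fatal/non-fatal shift analysis can show a shift that did not occur

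*SAP*

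**What the plan says.** All of the following is in SAP section A, Primary and Secondary Outcome Measures, unless stated otherwise.

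- **Fatal events.** A death counts if it occurs in a Rhode Island municipality, if "the final manner of death was deemed an accident", and if "a drug is listed on the death certificate as the primary cause of death or a significant contributing factor". No criterion mentions opioids.
- **Non-fatal events.** "Non-fatal overdoses will be defined as emergency medical services (EMS) runs for suspected non-fatal opioid overdoses", classified by the health department's modified case definition. Some criteria depend on naloxone rather than on a confirmed drug; the fifth needs only that "Narcan was given to the patient prior to EMS arrival". The SAP reports that "the modified case definition had a positive predictive value of 91.5" per cent for opioid-related incidents.
- **Use of the two halves.** Together they form the primary composite. In exploratory analyses they are examined separately, partly to see whether the intervention "produced shifts in the distribution of fatal and non-fatal events without affecting the overall incidence rate".

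The Protocol restricts neither half to opioids. Question 2 defines fatal overdoses as "accidental drug-related deaths deemed by a medical examiner to be attributed to a prescription or illicit drug" and non-fatal overdoses as emergency department visits for a suspected overdose; Questions 12.1 and 12.2 are similar. The difference in drug scope therefore arises only in the SAP. The SAP gives no reason for it and plans no analysis with matched scope. The sensitivity analyses in SAP section B concern Providence.

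**The concern.** Reading a change in the fatal/non-fatal mix as a change in lethality requires one kind of event that can end in either of two ways. Under the SAP, a fatal stimulant overdose is counted, but a survived one is counted only if a naloxone criterion happens to flag the run. Deaths without an opioid therefore have little or no counterpart on the non-fatal side.

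If the intervention acts mainly on opioid overdose, deaths that it cannot affect stay in the fatal count and nowhere else. The fatal IRR is then pulled towards 1 and the non-fatal IRR is not. An intervention that works equally well on fatal and non-fatal opioid overdose would look weaker against death, and the trial report could describe a shift that is only a product of the two definitions.

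**Working it through.** **Inputs.** The printed totals of SAP Table S1 (2016) are 1,461 non-fatal and 336 fatal events. Three further inputs are assumptions: a true IRR of 0.75 for all opioid events (the 25% reduction used in the SAP's power section), an IRR of 1 for non-opioid deaths, and a non-opioid share of deaths *q* of 10%, 30% or 50%.

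**The plan's own figure.** 1,461 + 336 = 1,797, which matches the SAP's figure of about 1,800 events a year. Deaths are 336/1,797 = 18.7% of the composite.

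**Formulas.**

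- Fatal IRR = *q* + (1 − *q*) × 0.75
- Non-fatal IRR = 0.75
- Ratio of IRRs = fatal IRR / 0.75 = 1 + *q*/3
- Composite IRR = 0.75 + 0.25 × *q* × 336/1,797
- Fatal share under intervention = 336 × fatal IRR / (336 × fatal IRR + 1,461 × 0.75)

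| *q* | Fatal IRR | Ratio of IRRs (true opioid value 1.00) | Composite IRR | Fatal share, control → intervention |
|---|---|---|---|---|
| 10% | 0.775 | 1.03 | 0.755 | 18.7% → 260.4/1,356.2 = 19.2% |
| 30% | 0.825 | 1.10 | 0.764 | 18.7% → 277.2/1,373.0 = 20.2% |
| 50% | 0.875 | 1.17 | 0.773 | 18.7% → 294.0/1,389.8 = 21.2% |

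The ratio of IRRs depends only on *q* and the assumed effects, not on Table S1. The town rows of Table S1 sum to 1,416 and 323 rather than to the printed totals. Using 323/1,739 in place of 336/1,797 leaves the composite IRRs unchanged to three decimals.

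**Power of the primary comparison.** This used the SAP's two-sample Poisson method with one year of follow-up, 5,000 stratified randomizations of the Table S1 towns, and two-sided alpha 0.05 (assumed, since the SAP states none). Power for a 25% reduction is 99.9% or more, consistent with the SAP's bound of at least 95%. With the diluted composite it stays at 99.7% or more. With opioid-involved deaths only (1,461 + (1 − *q*) × 336 = 1,763, 1,696 or 1,629 events a year) it stays at 99.8% or more. These figures ignore variation between towns, as the SAP's method does.

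**Size against chance.** SAP section B gives follow-up from 15 May 2022 to 15 August 2024, which is 27 months or 2.25 years. With equal arms and Poisson counts, the variance of the log ratio of IRRs is the sum of the reciprocals of the four expected counts. At *q* = 30% these are 168 × 2.25 = 378.0 and 378.0 × 0.825 = 311.9 deaths, and 730.5 × 2.25 = 1,643.6 and 1,643.6 × 0.75 = 1,232.7 non-fatal events. The standard error is 0.0853 and z = ln(1.10)/0.0853 = 1.12. The same calculation gives z = 0.38 at *q* = 10% and 1.83 at *q* = 50%.

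**The case against.** Much can be said for the plan, and most of it stands.

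- **The scopes overlap.** Opioid deaths are a subset of the deaths counted. The EMS definition is a screen for suspected opioid overdose: a positive predictive value of 91.5% means that about 8.5% of flagged runs are something else (0.085 × 1,461 ≈ 124, if that count applied to this definition, which Table S1 does not say). The two halves do not measure separate conditions.
- **The affected analysis is exploratory**, and randomization protects the comparison of arms within each component.
- **The false shift is modest.** In none of the scenarios does its expected z reach 1.96, and variation between towns would lower it further. The risk is a misleading estimate rather than a likely significant result.
- **The any-drug scope has a basis.** Protocol Question 12.1, Table 1, gives the prediction model's outcome as all unintentional drug-related deaths, and the trial tests targeting by that model.

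A reader might also infer that the contributing-factor wording brings in falls, drownings or crashes in which a drug played some part. The documents do not show this. The SAP introduces its criteria as defining drug-related deaths, its power section takes the deaths from the medical examiner's drug overdose death records, and Protocol Question 12.2 uses similar wording.

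None of this answers the remaining point: the SAP asks about a fatal/non-fatal shift without matching the two halves.

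**Conclusion.** The mismatch in drug scope is real, and its main consequence is confined to the exploratory shift analysis. With a true opioid IRR of 0.75, no effect on non-opioid deaths and an assumed non-opioid share of 10% to 50%, that analysis centres on a ratio of IRRs of 1.03 to 1.17 when the opioid value is 1.00. If the intervention reduced non-opioid deaths equally, the ratio would be 1.00. The result therefore rests on both the share and the absence of effect, and the documents give neither.

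A reader might conclude that the primary endpoint is compromised. It is not: the composite IRR moves from 0.750 to at most 0.773, and power by the SAP's method is essentially unchanged. Nor do the documents support narrowing the primary fatal definition. That would part it from the model outcome and alter the primary endpoint late: SAP section B dates the trial's start to November 2021, and section F places an interim efficacy analysis 18 months after launch.

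**What to change.** Keep the primary fatal definition and every planned analysis. In SAP section A, Primary and Secondary Outcome Measures, and in the analysis plan that section B says will be finalized before data analysis:

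1. Define a flag for opioid-involved deaths from the medical examiner's toxicology or cause-of-death data.
2. Run the shift analysis on opioid-involved deaths against the opioid EMS runs, and note that the EMS side remains a suspected diagnosis.
3. Report the composite with opioid-involved deaths only as a sensitivity analysis.
4. Describe the non-fatal half as suspected opioid overdose in the conclusions.

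**Cost.** The matched analysis has fewer deaths: on the 2016 total, 336 × (1 − *q*), or about 302, 235 or 168 a year at shares of 10%, 30% and 50%. The SAP says accidental deaths receive toxicological analysis, but neither document lists a drug-specific field among the data transferred, and Protocol Question 18 says partners share only the required variables. The field may have to be requested under the existing data use agreements.

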## **Study Sample**

This trial will not enroll individual participants. Randomization and assessment of study outcomes will occur at the municipal level, and all study outcomes will be assessed at this same level. However, during the study period, all persons who reside in Rhode Island or who experience a qualifying event—defined as a fatal or non-fatal overdose captured by the state’s multicomponent overdose surveillance system—may contribute data to either the PROVIDENT model or the study outcomes.

Based on 2016 data, we expect to observe approximately 1,800 events of fatal or non-fatal overdoses per year (see Table S1 below), which will be analyzed to evaluate the effects of the community-level intervention. Since all 39 cities/towns in Rhode Island will participate in the intervention trial, and due to the population-based nature of the fatal and non-fatal overdose surveillance system, every Rhode Island city and town may be eligible for inclusion in this study.

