## **Power Calculation and Sample Size**

To ensure adequate power, we will consider as the primary endpoint both fatal and non-fatal overdoses occurring at the municipal level. These events will be defined as described in the Primary and Secondary

Outcomes Measures above. These data are captured in the Rhode Island Office of the State Medical Examiner's drug overdose death records database and the Rhode Island Emergency Medical Services Information System. To estimate the power to detect significant differences between overdose rates in treatment and control cities/towns, we examined 2016 municipal-level overdose data. We used a stratified randomization scheme to conduct power simulations. Power was calculated for relative reductions in combined fatal/nonfatal overdose rates ranging from 15 to 30 percent. We used data from 2016 to set the underlying statewide overdose rate. We simulated randomization of each city to treatment versus control, estimated the expected number of events for each city based on population size and treatment assignment, and then used standard calculations for two-sample comparisons of Poisson rates. Due to the finite sample of municipalities with widely varying population sizes, the person-time of exposure in the control and treatment groups will vary depending on how cities are randomized. We therefore calculated power for several simulated randomizations, with 10 randomly selected instances shown (Figure S1). As shown, we will have at least 95% power to detect a >25% reduction in the treatment arm compared to cities/towns assigned to the control arm. These estimates are conservative: we assumed only one year of post-intervention follow-up time, whereas we anticipate two years based on the project timeline.

**Figure S1:** Power curves for the PROVIDENT trial from simulated randomizations (ten randomly selected instances are shown).

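### Whether deaths and non-fatal overdoses changed alike, or only the mix shifted, is to be judged from two separate analyses; the plan has no direct contrast and so no interval for the difference

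*SAP*

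**What the plan says.** SAP section A, Primary and Secondary Outcome Measures, makes the composite of fatal and non-fatal overdoses primary, "as the primary end-point in the trial to ensure adequate power". It then says that, in exploratory analyses, "we will examine the effect of the intervention on overdose fatalities and non-fatal overdoses separately". The stated purpose is "to determine whether the intervention produced similar changes in rates of each outcome, and/or produced shifts in the distribution of fatal and non-fatal events". The shift of interest is one that leaves the total unchanged: "shifts in the distribution of fatal and non-fatal events without affecting the overall incidence rate".

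SAP section B, Analysis, defines one effect measure, the composite incidence rate ratio. It comes from a mixed model with town-level random intercepts and slopes, with bootstrap 95% intervals. Neither that section nor the protocol's analysis text for the cluster trial gives a ratio of the two rate ratios, an event-type by arm term, or a model for the fatal share of events. No rule is written for how the two separate results will be compared. Section B also says that the analysis plan will be finalised and posted before analysis starts.

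The only power statement concerns the composite: "we will have at least 95% power to detect a >25% reduction in the treatment arm".

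**The concern.** Similar changes and a shifted mix are both statements about how one effect compares with another. Two separate estimates give a point estimate of their ratio by division, but no interval for it. Deaths and non-fatal events also arise in the same towns. A town-level change that moves both outcomes inflates each separate standard error but largely drops out of their difference, so two wide separate intervals can hide a difference that the data could show.

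The question matters here. The forecasting model predicts deaths only, while about 81% of the Table S1 events are non-fatal (1,461 of 1,797). A fall in deaths offset by more survived overdoses would leave the composite near null, and this exploratory analysis is where the plan would look for it.

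**Working it through.** **Inputs.** Table S1 Total row (2016): 336 deaths and 1,461 non-fatal overdoses, or 1,797 a year, in line with the SAP's figure of about 1,800. The 39 rows sum to 323 and 1,416; using those sums moves the plain Poisson results by about 2 points or less. Follow-up: 1 year for the power calculation, 27 months (2.25 years) for the analysis. Baseline: 5 years. Assumed, because the documents do not state them: two-sided 5% level, and the SD of town log-changes.

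**Step 1. The plan's own figure.** With E control-arm events, SE(log IRR) = √(1/E + 1/(E × IRR)) and power = Φ(|log IRR|/SE − 1.96). For the composite at 1 year, E = 1,797/2 = 898.5 and IRR = 0.75, so SE = 0.051, z = 0.2877/0.051 = 5.6 and power is above 99.9%. Across stratified randomisations of Table S1 it is 99.93% to 99.99%. The stated floor of 95% holds.

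**Step 2. Plain Poisson, the two outcomes separately.** For a total-preserving shift with deaths IRR r, the non-fatal IRR is 1 + (1 − r) × 336/1,461. At r = 0.75 this is 1.0575. Worked at 2.25 years:

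- Deaths: E = 336 × 2.25/2 = 378, SE = 0.0786, z = 3.66, power 96%.
- Non-fatal: E = 1,461 × 2.25/2 = 1,644, SE = 0.0344, z = 0.0559/0.0344 = 1.63, power 37%.
- Neither significant: (1 − 0.956) × (1 − 0.369) = 3%.
- Direct contrast: SE = √(0.0786² + 0.0344²) = 0.0858, z = log(1.0575/0.75)/0.0858 = 0.3436/0.0858 = 4.0, power 98%.

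| Deaths IRR | Years | Shift: neither significant | Shift: direct test | Equal effects: one significant, one not |
|---|---|---|---|---|
| 0.85 | 1 | 64% | 35% | 64% |
| 0.80 | 1 | 44% | 56% | 51% |
| 0.75 | 1 | 26% | 76% | 32% |
| 0.85 | 2.25 | 36% | 65% | 43% |
| 0.80 | 2.25 | 13% | 89% | 18% |
| 0.75 | 2.25 | 3% | 98% | 4% |

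**Step 3. Adding baseline noise and town variation.** Simulated trials used the Table S1 rows, stratified randomisation, Poisson counts by town and event type for 5 baseline and 2.25 follow-up years, a precision-weighted contrast of town log-changes, and critical value 2.02. This stands in for the planned mixed model; it is not that model. Baseline noise alone raises the variance for deaths from 0.0786² = 0.0062 by 2/840 to 0.0086 (840 = 336 × 5/2). Together with unequal arms, this is why the SD 0 result below is 15% and not 3%.

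| Shared town SD (assumed) | 0 | 0.1 | 0.2 | 0.3 |
|---|---|---|---|---|
| Shift (0.75 / 1.06): neither significant | 15% | 27% | 46% | 64% |
| Shift: direct test rejects | about 85% | about 85% | about 85% | about 85% |

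If a town's two log-changes also differ from each other with SD 0.1, the direct test detects the shift in about 75%. With equal effects of 0.75, one outcome is significant and the other not in about 21% at SD 0 and 34% to 42% at SD 0.1 to 0.3; the direct test rejects in about 4%.

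**Step 4. Why the direct test is stable.** As the shared SD goes from 0 to 0.3, the SE for deaths rises from 0.10 to 0.16 and for non-fatal events from 0.04 to 0.13. The SE of the direct contrast stays at 0.11. Combining the two separate SEs as if independent at SD 0.3 would give √(0.16² + 0.13²) = 0.21, nearly twice too large.

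**Step 5. The limit of that gain.** Cancellation needs shared variation. In a simpler event-weighted calculation with variation wholly independent between outcomes (2.25 years, r = 0.75), direct power is 77% at SD 0.1 and 39% at SD 0.2. The direct interval is then wide, and correctly so.

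**The case against.** **The analysis is exploratory and no reading rule is written.** This stands. The SAP does not say that similarity will be judged by overlapping intervals or matching significance, so the misreading rates above are illustrations, not properties of the plan. A confirmatory standard is not called for. An equivalence margin would also decide the answer by itself: with a direct SE of 0.105 and truly equal effects, similarity could be claimed in 8% of trials at 0.80 to 1.25 and in 93% at 0.67 to 1.50. But the exploratory label limits the strength of a claim. It does not make two separate estimates answer a question about their difference.

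**A reader might infer that a real shift would usually pass as similar and that equal effects would often look different.** The documents do not support that. The two halves rely on different reading rules: under interval overlap, equal effects look different in under 1% of trials; under significance, both results are null under the 0.75/1.06 shift in more than half of trials only at SD 0.3, the top of an assumed range. Nor are deaths few in absolute terms: 336 × 2.25 = 756 are expected at the 2016 rate.

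**The direct contrast has its own hazard.** Deaths cover any drug, whereas the SAP's non-fatal events are opioid-related EMS runs. From June 2023 Providence sent all overdose 911 calls to EMS, and it holds 449/1,416 = 32% of the Table S1 non-fatal row counts. If that raised its non-fatal counts by 20% or 30% on average (assumed), then with equal effects and shared SD 0.2 the direct test rejected in 14% or 23% of trials, or 7% or 11% when an outcome-specific SD of 0.1 was modelled. This stands and shapes the fix.

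**The final plan is still to be posted.** It may add the contrast. The current text names only separate analyses.

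**Conclusion.** The concern holds in limited form. For a comparative question the SAP names only separate analyses, and neither document specifies a direct contrast or an interval for the difference. Side-by-side reading can mislead. For the 0.75/1.06 shift at 2.25 years, neither result is significant in about 15% to 64% of simulated trials, against about 85% detection by a direct test (about 75% with some outcome-specific variation). For equal effects of 0.75, the two results disagree on significance in about 21% to 42%, against about 4% rejection by the direct test.

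These sizes rest on 2016 counts, an assumed shared town SD of 0 to 0.3, a 5% level, and a significance-based reading that the SAP does not prescribe. With no town or baseline variation and a 25% effect, both misreadings fall to 3% to 4%. The primary composite analysis is not affected.

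**What to change.** In SAP section A, Primary and Secondary Outcome Measures, add one prespecified contrast, labelled exploratory: the ratio of the fatal to the non-fatal IRR with its 95% CI. It can come from any of these:

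- a joint model with an event-type × arm × period term that allows outcome-specific town variation;
- a binomial mixed model of the fatal fraction by town and period, with the same allowance;
- a bootstrap that resamples municipalities with both outcomes together.

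Base any statement about similarity or a shift on that interval, read together with the composite IRR and its CI. Keep the separate estimates as description. Repeat the contrast under the Providence sensitivity analysis in section B, because the June 2023 change can alter non-fatal counts alone.

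The cost is SAP wording and one extra model on data already held. The downside is that the interval may be too wide to support a claim of similarity, and the report would then have to say so.
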